## 6.12. Safety Analyses

The general analysis of safety has been described in the H0P-MC-CPMP SAP Version 5. However, additional ISA-specific safety considerations are described in the sections below.

### 6.12.1. Extent of Exposure

The cumulative dosage taken during the double-blind treatment period will be summarized. In addition, the distribution of the number of doses received during the double-blind treatment period will be summarized by reporting the number and percent of participants in the safety population who received 1, 2, 3, or 4 infusions during the double-blind treatment period.

Duration of exposure to study drug (defined as the time since first injection of the study treatment in days) will be summarized by treatment group using descriptive statistics; the summary will also include the total exposure in patient years.

Duration of exposure (days):

*= Date of last study visit (scheduled or unscheduled) during the double blind treatment period – Date of first injection of the study treatment + 1*

Total exposure in patient years will be calculated as follows:

*Total exposure in patient years = Sum of duration (days) of exposures for all patients in the treatment group/365.25*

### 6.12.2. Adverse Events

The general analysis of adverse events has been described in the H0P-MC-CPMP SAP Version 5.

This ISA will also consider post-treatment-emergent adverse events due to the long follow-up period.

A post-treatment-emergent adverse event (PTEAE) is defined as an event that first occurs or worsens in severity after treatment discontinuation and on or before study discontinuation. The Medical Dictionary for Regulatory Activities (MedDRA) Lowest Level Term (LLT) will be used in the post-treatment-emergent computation. The maximum severity for each LLT during the treatment period will be used as a reference.

The baseline of PTEAE is from the first dosing date to the treatment disposition in the double-blind treatment phase. The post-treatment follow-up period will be included as postbaseline for this analysis. While unusual, it is possible to have a missing severity for events. Events with a missing severity during the post-treatment period will be treated as “severe” and post-treatment emergent events will be determined by comparing with treatment period. All events occurring after the day of treatment discontinuation will be treated as post-treatment period.

[figure not shown]
PTEAEs will be summarized by preferred term and by preferred term within system organ class in participants who received LY3016859.

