1.1. Synopsis

Protocol Title:

Randomized, placebo-controlled, Phase 2 clinical trial to evaluate LY3016859 for the treatment of osteoarthritis

Rationale:

The purpose of this study is to test whether LY3016859 is efficacious in relieving knee pain due to osteoarthritis (OA). LY3016859 is a high affinity humanized immunoglobulin G (IgG)₄ monoclonal antibody that binds to key residues in the C-terminal regions of transforming growth factor- α (TGF- α) and epiregulin, preventing their binding to the epidermal growth factor receptor (EGFR).

Data will be collected to assess the safety, and tolerability of LY3016859 in this study population. Pharmacokinetic (PK) properties, pharmacodynamic (PD) effects and immunogenicity profile will also be explored. The totality of data from this proof-of-concept study will assess the benefits and risks associated with LY3016859 and inform decisions for the clinical development of LY3016859.

Objectives and Endpoints

The primary and secondary objectives and endpoints are stated in the master protocol H0P-MC-CPMP (CPMP) and OA disease-state addendum (DSA; H0P-MC-CPMP[1]).

Overall Design

This is a 26-week, Phase 2, randomized, double-blind, placebo-controlled study that will compare LY3016859 versus placebo in participants with OA in the knee.

Disclosure Statement: This is a randomized, investigator- and participant-blind, placebo-controlled, Phase 2 clinical trial.

Number of Participants:

Approximately 125 participants will be randomly assigned to study intervention (84 LY3016859 and 41 placebo) with the assumption that 15% of the participants will drop out prior to the end of the double-blind treatment period.

Intervention Groups and Duration:

This 26-week study includes an 8-week double-blind treatment period and an 18-week follow-up period.

[figure not shown]
Participants will receive an intravenous (IV) infusion every 2 weeks for a total of 4 infusions.

Intervention Name	LY3016859	Placebo
Dosage Level(s)	750 mg starting dose 500 mg subsequent doses	Not applicable
Route of Administration and duration	1 hour IV infusion	1 hour IV infusion

Participants will be monitored for at least 4 hours after completion of each infusion.

Data Monitoring Committee: Yes

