**6.19. Clinical Trial Registry Analyses**

Additional analyses will be performed for the purpose of fulfilling the Clinical Trial Registry (CTR) requirements.

Analyses provided for the CTR requirements include the following:

Summary of adverse events, provided as a dataset, which will be converted to an XML file. Both Serious Adverse Events and 'Other' Adverse Events are summarized: by treatment group, by MedDRA preferred term.

- A serious adverse event is an adverse event that is considered 'Serious' whether it is a treatment emergent adverse event (TEAE).
- An adverse event is considered in the 'Other' category if it is both a TEAE and is not serious. For each Serious AE and 'Other' AE, for each term and treatment group, the following are provided:
  - the number of participants at risk of an event
  - the number of participants who experienced each event term
  - the number of events experienced.
- Consistent with [www.ClinicalTrials.gov](http://www.ClinicalTrials.gov) requirements, 'Other' AEs that occur in fewer than 5% of participants in every treatment group may not be included if a 5% threshold is chosen (5% is the minimum threshold).
- AE reporting is consistent with other document disclosures for example, the CSR, manuscripts, and so forth.

A summary of a baseline characteristics XML file will be provided.

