## 8. Reports to be Generated at Final Database Lock

The following analysis will be performed for final database lock.

- Patient disposition - the analysis of patient disposition conducted in POC lock will be conducted for double-blind treatment and safety follow-up period combined.
- eCOA compliance - the overall eCOA compliance analysis conducted in POC lock will be summarized for the PDEP period plus at each nominal week up to Visit 801.
- Concomitant therapy – the analysis conducted in POC lock will be repeated including safety follow up period combined (may also include PDEP) except the listing of rescue medication use above protocol specified limits.
- Efficacy endpoint – The weekly average pain intensity via NRS will be calculated with extension to week 12 (Visit 801). The following analysis will be conducted across all time points in the double-blinded treatment and safety follow-up period combined (DB plus FU) based on the same model conducted in DB treatment period only.
  - Change from baseline in average pain intensity measured by weekly average of NRS
  - Change from baseline in worst pain intensity measured by weekly average of NRS
  - Change from baseline in DSA-specific physical functioning measures
  - Proportion of participants with a pain reduction from baseline greater than or equal to 30%, 50%, and 70% as measured by the average pain responses on the NRS
  - Proportion of participants with reduction from baseline greater than 30%, 50%, and 70% on DSA-specific physical function subscale
  - Overall improvement as Measured by Patients' Global Impression of Change (PGI)

A frequentist MMRM analysis will be conducted as a sensitivity analysis for the primary and some secondary endpoints.

A Bayesian MMRM subgroup analysis of baseline pain severity ( $<7$ ,  $\geq 7$ ) will be also evaluated for the primary and key secondary endpoint. A frequentist MMRM analysis will be performed as a sensitivity analysis for subgroup analysis.

- Safety analyses for TEAEs – the following analysis will be repeated including double-blind and safety follow-up period unless otherwise specified.
  - Overview of adverse event
  - SAE and a listing of SAE

- TEAE and Post-treatment emergent adverse event (PTEAE) by PT, by PT within SOC. A listing of TEAE and PTEAE will be provided.
- Post-treatment emergent AE by PT, by PT within SOC for safety follow-up period only
- Adverse event of special interest (ISA specific)

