- Laboratory measures – the analysis conducted in POC lock will be repeated in DB plus FU period. The additional analysis will be included
  - The shift table of eGFR at baseline vs. postbaseline by minimum, maximum and last observed eGFR result will be summarized.
  - Summary of treatment-emergent ADA positive anytime in DB treatment period by ADA positive titer status at the last non-missing assessment in safety follow-up period will be presented by treatment.
  - A shift table of ADA from maximum baseline ADA titer to maximum postbaseline ADA titer in LY3016859 arm will be reported.
  - A listing of participants with ADA Detected at any time for safety population will be provided.
  - Summary of hepatic function laboratory maximum observed result will be presented.
- Vital signs – the analysis conducted in POC lock will be repeated for combined DB plus FU period.
- ECG - the analysis conducted in POC lock will be repeated for combined DB plus FU period. Additionally, a summary of ECG measures and boxplot will be provided as well as a listing of out of range of ECGs.
- Protocol deviations - the analysis conducted in POC lock will be repeated for combined DB plus FU period.

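### SAP Section 6.12.2 tabulates post-treatment-emergent adverse events for LY3016859 recipients only, although placebo participants have the same 18-week follow-up with adverse events collected

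*SAP*

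**What the plan says.** SAP Section 6.12.2 refers general methods to the master-protocol SAP ("The general analysis of adverse events has been described in the H0P-MC-CPMP SAP Version 5") and then adds an analysis specific to this appendix: "This ISA will also consider post-treatment-emergent adverse events due to the long follow-up period". Its definition of a PTEAE names no arm. The table sentence does: "PTEAEs will be summarized by preferred term and by preferred term within system organ class in participants who received LY3016859". No reason is given for leaving placebo out.

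SAP Section 8, on the final database lock, has two PTEAE lines: "TEAE and Post-treatment emergent adverse event (PTEAE) by PT, by PT within SOC. A listing of TEAE and PTEAE will be provided" and "Post-treatment emergent AE by PT, by PT within SOC for safety follow-up period only". Neither mentions treatment group or a limit to LY3016859.

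The follow-up is described for the study as a whole. Protocol Section 1.1 states: "This 26-week study includes an 8-week double-blind treatment period and an 18-week follow-up period". Protocol Section 4 and SAP Section 5.1 require Visits 801 to 803 of participants generally. The Schedule of Activities (Protocol Section 1.3) has a single adverse-event row, marked at all three visits.

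**The concern.** The reason given for the analysis, a long follow-up, applies equally to both arms, but the tables cover only one. A reader of an LY3016859-only table cannot tell how many of the events would have occurred anyway.

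Three features of this period make single-arm counts hard to read:

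- **Residual drug is plausible early in follow-up.** Protocol Section 2.2 reports a terminal half-life approaching 18 days at higher doses.
- **Other treatment may change.** Protocol Section 2.3.1 allows standard osteoarthritis treatment to restart after Visit 801, which can bring events unrelated to study drug.
- **Missing severity counts as severe.** Section 6.12.2 applies this rule to post-treatment events. It can only raise the count, and a single-arm table cannot show whether both arms are affected alike.

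At stake is the descriptive safety profile after dosing, mainly for non-serious events. The primary and key secondary analyses are not involved.

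**Working it through.** **1. Inputs and the plan's own figures.**
- Randomised: 84 LY3016859 and 41 placebo, total 125 (Protocol Section 1.1).
- Dropout: 15% before the end of double-blind treatment (same section). 125 × 0.85 = 106.25, against about 107 completers stated in SAP Section 5.2. This agrees within rounding.
- By arm: 84 × 0.85 = 71.4 and 41 × 0.85 = 34.9, so about 71 and 35.
- Follow-up: 26 − 8 = 18 weeks, or 18/26 = 69% of the study.
- Early discontinuers also contribute some follow-up, because Visit 801 is scheduled about 30 days after their last dose. The placebo denominator therefore lies between about 35 and 41.

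**2. What the restriction leaves out.** The share is 41/125 = 32.8% of participants. Scheduled placebo follow-up is 41 × 18 × 7 / 365.25 = 14.1 patient-years, or 12.0 if 15% drop out and contribute none.

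**3. Residual drug.** The last infusion is at Week 6. With simple exponential decay at the 18-day upper value, the fraction of the Week 6 level remaining is:
- Week 12: 2^(−42/18) = 0.198
- Week 16: 2^(−70/18) = 0.068
- Week 26: 2^(−140/18) = 0.005

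**4. What a placebo column could show.** The documents give no background rates, so 2%, 5% and 10% for a single preferred term are assumptions, equal in both arms. Expected cases are n × p. The chance of no placebo case is (1 − p)^n. The half-width is that of the Newcombe 95% interval for the difference, averaged over the two binomial distributions.

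| Assumed rate | Expected cases, 71 vs 35 | P(no placebo case), n = 35 | P(no placebo case), n = 41 | Mean half-width, 71 vs 35 | Mean half-width, 84 vs 41 |
|---|---|---|---|---|---|
| 2% | 1.4 vs 0.7 | 49% | 44% | 8.9 points | 7.9 points |
| 5% | 3.6 vs 1.8 | 17% | 12% | 10.7 points | 9.6 points |
| 10% | 7.1 vs 3.5 | 2.5% | 1.3% | 12.9 points | 11.8 points |

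**5. Hypothetical example.** Suppose 6 of 71 LY3016859 participants have one term: 8.5%, exact 95% interval 3.2% to 17.5%. The single-arm table looks the same in both of these cases:
- Placebo 3/35 (8.6%): difference −0.1 points, 95% interval −14.6 to 10.3.
- Placebo 0/35: difference 8.5 points, 95% interval −2.4 to 17.2.

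**6. Is the gap filled elsewhere?** In part.
- The Section 8 listing has no LY3016859-only limit.
- Section 8 repeats the adverse-event overview, serious-event and special-interest outputs over follow-up.
- SAP Section 6.19 gives serious events by treatment group for the registry. Its non-serious category takes an event only "if it is both a TEAE and is not serious", so non-serious PTEAEs do not enter through that route.

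What is left without a stated by-arm summary is chiefly non-serious PTEAEs by preferred term.

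**The case against.** The strongest reply is that Section 8 is the list of final-lock deliverables and does not carry the restriction. Its first PTEAE line puts PTEAEs beside treatment-emergent events, which the SAP nowhere limits to one arm. The master-protocol SAP Version 5 was not available for this review and may set treatment columns by default. Both points limit what can be claimed: the documents do not prove that the final tables will lack a placebo column. They do not remove the problem, because Section 6.12.2 holds the only explicit statement of who is in these tables. Section 8 is silent on arm for other outputs as well, so its silence cannot be read as lifting the limit. The two sections do not contradict each other; one is specific and the other says nothing. The text extraction also marks a missing figure just before the restricting sentence. Its content is unknown and nothing is inferred from it.

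A second reply is that the column would be of little use. The half-widths are about 8 to 13 points, both intervals in the example include zero, and by Week 16 little drug remains. The 18-day half-life is itself an upper value, and under target-mediated disposition decay should be faster at low concentrations. Restarted treatment and unequal dropout could also weaken the comparison. All of this stands, and it is why the column should be descriptive. It does not favour showing one arm alone, where the reader has no reference at all.

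It is also true that no stated decision turns on PTEAEs. The key safety events in SAP Section 6.17 include no PTEAE output, and a by-arm count could be made later from the listed data.

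**Conclusion.** The concern holds for SAP Section 6.12.2. Followed as written, its PTEAE tables have no concurrent background rate, although 41 of 125 participants (32.8%) are on placebo with the same scheduled follow-up and adverse-event collection. The consequence is moderate: a gap in descriptive safety reporting, chiefly of non-serious events by preferred term, with no effect on efficacy or sample size. It is worth correcting because correction is cheap.

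The precision figures rest on assumed background rates of 2% to 10% and on 15% dropout in each arm. The residual-drug figures rest on simple exponential decay at an 18-day half-life. The finding itself needs none of these: it follows from the wording of Section 6.12.2 and the shared schedule. Confidence is medium, because the master-protocol SAP could not be checked for a default grouping.

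**What to change.** Reword the Section 6.12.2 sentence so that PTEAEs are summarised by treatment group (LY3016859 and placebo), by preferred term and by preferred term within system organ class, with the denominator for each arm. Put the same treatment-group wording in both PTEAE lines of Section 8. State that the comparison is descriptive.

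The cost is one sentence, matching words in Section 8 and one added table column. No new data are needed, since adverse events are already collected in follow-up without restriction by arm. Section 8 already has one follow-up output by arm: the anti-drug antibody titer status "in safety follow-up period will be presented by treatment". The drawback is small placebo counts (about 35 to 41 participants, often no case of a rare term), which should not be over-read.

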### **6.12.3. Deaths, Other Serious Adverse Events, and Other Notable Adverse Events**

The general summary of adverse of events is described in the H0P-MC-CPMP SAP Version 5.

Treatment emergent adverse events of special interest will be summarized separately by preferred term. These events include

- infusion site reactions (preferred MedDRA term)
- hypersensitivity and infusion-related reactions
  - Anaphylactic reaction (SMQ)
  - Anaphylactic/anaphylactoid shock conditions (SMQ)
  - Angioedema (SMQ)
  - Hypersensitivity (SMQ)
  - Infusion-related reaction (preferred MedDRA term)
- dermatological adverse events
  - Severe cutaneous adverse reactions (SMQ)
  - Drug reaction with eosinophilia and systemic symptoms syndrome (SMQ)
- abnormal renal function
  - Renal function analyses (MedDRA HLT)
  - Renal failure and impairment (MedDRA HLT)

A large, stylized logo consisting of the letters 'C', 'C', and 'I' in a red, serif font. The letters are set against a solid black rectangular background that covers most of the page.

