6.1.1.2. Management of Infusion Reactions

All participants should be monitored closely, as there is a risk of infusion reaction and hypersensitivity (including anaphylaxis) with any biological agent.

Symptoms and Signs

Symptoms and signs that may occur as part of an infusion reaction include, but are not limited to fever, chills, nausea, headache, bronchospasm, hypotension, angioedema, throat irritation, rash, pruritus, myalgia, and dizziness.

Site Needs

The clinical site should have necessary equipment and medications for the management of any infusion reaction, which may include but is not limited to oxygen, IV fluid, epinephrine, acetaminophen and antihistamine.

Management of Infusion Reactions

Investigators should grade the severity of the infusion reaction and manage infusion reactions based on standard of care and their clinical judgment. If an infusion reaction occurs, then supportive care should be used in accordance with the signs and symptoms.

This table outlines guidance when a mild to moderate infusion reaction occurs.

If...	Then...
a mild to moderate infusion reaction occurs	the infusion rate should be slowed or stopped depending on the symptoms or signs present. For example, reducing the rate by 50% from 2 mL/minute to 1 mL/minute.
the infusion rate is slowed	
 the infusion should be completed at the slower rate, as tolerated. subsequent infusions may be administered at the discretion of the investigator in agreement with the Lilly medical monitor.
the infusion rate is slowed, and subsequent infusions are continued	the infusion rate must be maintained at the slowest tolerated rate used.

The study intervention infusion should be stopped immediately and permanently if it is an infusion reaction

- with systemic involvement, including, but not limited to significant treatment emergent hypotension, bronchospasm, or wide-spread urticaria
- that does not respond to a slower infusion rate or oral medications
- that is determined as clinically significant by the investigator.

If a participant permanently discontinues from study intervention, they should complete AE monitoring and other procedures as stated in Section 4, Study Design, and the CPMP and OA01 SoAs.

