8.2. Adverse Events and Serious Adverse Events

8.2.1. Infusion Site Reactions

Symptoms of a local infusion site reaction may include erythema, induration, pain, pruritus, and edema. If an infusion site event is reported, the AE will be recorded, and additional data will be provided to the sponsor in the CRF.

Additional blood and urine samples should be collected as described in OA01 Section 10.3, Appendix 3, “Recommended Laboratory Testing for Hypersensitivity Events”. Laboratory results are provided to the sponsor via the central laboratory.

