**Hypersensitivity**

- Moderate to severe infusion site reactions
- Serious or severe hypersensitivity reactions

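### SAP 6.12.3 identifies infusion site reactions at preferred-term level only, so a local event coded as a symptom can be left out of the special-interest table

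*SAP*

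**What the plan says.** SAP section 6.12.3 introduces its list with "Treatment emergent adverse events of special interest will be summarized separately by preferred term. These events include". The entries are searched at different MedDRA levels:

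- Infusion site reactions: "infusion site reactions (preferred MedDRA term"). Nothing else is given.
- Hypersensitivity and infusion-related reactions: four SMQs, among them "Hypersensitivity (SMQ"), plus "Infusion-related reaction (preferred MedDRA term").
- Dermatological events: two SMQs.
- Renal events: two HLTs, one of them "Renal failure and impairment (MedDRA HLT").

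Protocol section 8.2.1 states: "Symptoms of a local infusion site reaction may include erythema, induration, pain, pruritus, and edema". An infusion site event is recorded as an AE, with further data in the CRF. For the systemic reaction, protocol section 6.1.1.2 begins: "Symptoms and signs that may occur as part of an infusion reaction include, but are not limited to fever, chills, nausea, headache, bronchospasm, hypotension", and names 12 symptoms or signs in all. Protocol section 8.2.2 asks for CRF data on each symptom of such a reaction.

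The Hypersensitivity domain of SAP section 6.17 has two items. One is "Moderate to severe infusion site reactions"; the other covers hypersensitivity reactions that are serious or severe. Neither has a search definition, and infusion-related reactions are not named there.

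**The concern.** A preferred term is a single code, whereas an HLT or SMQ gathers many. If a site reports pain or induration at the infusion site and the report is coded to that symptom, a search on one umbrella term does not find it. The plan uses grouped searches for every other group, and the protocol already collects dedicated CRF data on these reactions, but the infusion site line uses neither.

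Protocol section 2.3.1 names infusion and hypersensitivity reactions as a potential risk of clinical significance, with monitoring as the mitigation. The special-interest table is where a reader looks for the result of that monitoring. An incomplete count there, and possibly in the 6.17 safety totality, would make local tolerability look better than it was. If the line was meant more broadly, two programmers could still produce different tables from it.

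**Working it through.** The plan states no figure on this point, so there is nothing to reproduce. The check is to trace kinds of report through the searches as written.

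| What the site reports and coding assigns | Infusion site line | Other searches in 6.12.3 |
|---|---|---|
| The local reaction itself, symptoms held as CRF detail | Found | Not needed |
| Local pain or induration, coded as the symptom | Not found, read literally | None aimed at it |
| Local erythema, pruritus or edema, coded as the symptom | Not found, read literally | Possibly an SMQ; SMQ content is not in the documents |
| Systemic reaction reported under the reaction term | Not applicable | Found by the infusion-related preferred term |
| Angioedema or another allergic-type symptom without the reaction term | Not applicable | The SMQs are, on their face, aimed at these |
| Fever, chills, nausea, headache or myalgia without the reaction term | Not applicable | No search evidently aimed at these |

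The gap is therefore clearest for local symptoms. For systemic reactions it is confined to non-allergic symptoms reported without the reaction term.

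**Safety totality (SAP 6.17).** The local-reaction item is affected only if it uses the 6.12.3 search, which the SAP does not say. Infusion-related reactions are not a named item, so their preferred term cannot remove them from it. Related SAEs, and study or treatment discontinuations due to an AE, are counted whatever the term. What can be lost is a moderate or severe local reaction that neither counts as a related SAE nor leads to discontinuation.

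**Illustration of scale, on assumptions only.** Take 84 LY3016859 participants (protocol synopsis). Let *r* be the true proportion with a local reaction, and *s* the share of those with at least one report under the searched term. Both are assumed. The expected count is 84 × *r* × *s*:

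| *r* | *s* = 100% | 75% | 50% | 25% |
|---|---|---|---|---|
| 5% | 4.2 | 3.2 | 2.1 | 1.1 |
| 10% | 8.4 | 6.3 | 4.2 | 2.1 |
| 20% | 16.8 | 12.6 | 8.4 | 4.2 |

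At *r* = 5%, the chance that the table shows no case is (1 − 0.05)^84 = 0.013 with full capture, and (1 − 0.05 × 0.5)^84 = (0.975)^84 = 0.12 with *s* = 50%. At *s* = 100% nothing is lost, whatever the rate.

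**Between arms.** If *s* is the same in both arms, the observed difference is *s* × (rate on LY3016859 − rate on placebo), and the observed ratio is unchanged.

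**The case against.** The strongest reply is that no loss is established, only loose wording.

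- **The plural.** The infusion site entry is plural, the infusion-related entry is singular, and the table is by preferred term. The plural may mean the set of infusion site terms. That is a fair reading. It leaves the line ambiguous, and it still needs a term list.
- **Recording rules.** Protocol 8.2.1 and 8.2.2 can be read as making the reaction the AE, with symptoms as supplementary CRF data. Under that practice little or nothing is lost. Neither document states the coding convention, so the loss is conditional.
- **General tables.** SAP section 8 provides TEAEs by preferred term, by preferred term within system organ class, and in a listing. A reader might infer that symptom-coded reactions vanish from the safety report. They do not; they are missing only from the grouped table.
- **Infusion-related reactions.** A reader might infer that they share the same fault, since they too have a preferred term. The documents do not support that, because four SMQs sit in the same group.
- **Direction of bias.** A reader might infer that LY3016859 is flattered in particular. No document gives local reaction rates by arm, and placebo participants also receive one-hour infusions. Equal under-capture shrinks the absolute difference only if the true rates differ.
- **Unseen text.** Text after the 6.12.3 list is blacked out, and the CPMP SAP Version 5, to which general AE and totality methods are deferred, is not available here. Either could hold a fuller definition.

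What stands is that the visible infusion site line has no term list or grouped level, unlike the rest of the list, and makes no use of CRF data collected for this purpose.

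**Conclusion.** The concern holds for the infusion site line. As literally written, a local event coded as a symptom is left out of the special-interest table, and out of the 6.17 local-reaction item if that item shares the search. For infusion-related reactions the gap is narrow: non-allergic symptoms reported without the reaction term.

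This rests on reading the entry as one term and on at least some sites or coders recording the symptom rather than the reaction. The documents settle neither, and they give no incidence or coding share, so the size cannot be estimated; the figures above show only how counts would scale. The effect is on the grouping of events in a descriptive safety table and possibly one totality item. It does not mean that events go unreported or that one arm is favoured. The change is still worth making, because it replaces an incomplete or ambiguous rule with one that can be programmed, using data already collected.

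**What to change.** 1. In SAP 6.12.3, define infusion site reactions as all preferred terms under the MedDRA grouping for infusion site reactions, or any AE for which the protocol 8.2.1 CRF data were completed. State the MedDRA version and attach the resulting term list.
2. In SAP 6.17, say that the infusion site item uses this definition, restricted to moderate and severe events.
3. For infusion-related reactions, keep the four SMQs and the preferred term, and add any AE with the protocol 8.2.2 CRF data completed.
4. If the CPMP SAP Version 5 already defines these searches, a cross-reference to it is enough.

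The cost is a few lines of SAP text and a change to the special-interest programming; no new data are needed. The broader search will bring in some trivial local events, which a breakdown by severity makes visible. If the change is made after the proof-of-concept unblinding, date it and show the existing tabulation beside the new one.
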